## 1. Objectives

The objective of this study is to obtain the cerebral regional oxygen saturation (cRSO2) in a preterm population that is born at altitude to determine if the range of “normal” values is different than those obtained at sea level. **We hypothesize that the cRSO2 will be lower than the normative values that have been previously described.** As more clinical studies are being performed, and the use of NIRS becomes more common, it is imperative that we assess if other factors such as altitude must be considered prior to general implementation.

**Aim 1:** We will prospectively obtain cRSO2 for the first 96 hours of life in infants born <32 weeks’ gestation. The data obtained will not be interrupted clinically as the clinicians will not be able to view the data obtained from the NIRS monitoring.

**Aim 2:** Outcome measures including death, intraventricular hemorrhage, necrotizing enterocolitis, sepsis, duration of supplemental oxygen required, time to taking full volume feeds via nipple, and hospital length of stay will be collected. This will be compared with the infant’s average cRSO2 as well as the fluctuation in cRSO2 that was observed. This may provide supportive evidence for clinical use of NIRS in future trials at UNMH.

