## 2. Background

Near-infrared spectroscopy (NIRS), is a technology that can provide continuous, non-invasive monitoring of oxygenation in tissue[1]. Light absorption is measured at a few discrete wavelengths which can provide information for the tissue oxygen saturation in multiple organs[2], with cerebral, renal and splanchnic oxygenation being the most commonly measured in neonates[1]. NIRS technology was first available in 1977, however different sensors and manufacturers resulted in a large range of regional oxygen saturation (RSO2), making it difficult to establish normative values within a specific population[1]. Thus, improvements in the technology has resulted in the ability to consider more clinical uses for the NIRS technology.

Infants with congenital heart disease is a population in which the NIRS technology has been applied. The use of cerebral oximetry measurement has provided the first indication of a clinical problem in 23% of the procedures in which the technology was utilized[1]. While some initial studies have shown a negative correlation between cerebral regional oxygen saturation (cRSO2) and gestational age[3], routine use in the preterm infant has not been established.

Infants born prematurely (<37 weeks’ gestation), and especially those born extremely preterm (<28 weeks’ gestation), have organs that are immature and vulnerable. There are fluctuations in cerebral blood flow due to limitations in autoregulation, which may be exacerbated by routine care of the infant[4]. Previously there was a limitation in the ability to monitor these changes in blood flow and saturations, however NIRS now provides the technology needed. There are clinical trials ongoing to assess cRSO2 immediately after birth in an attempt to improve outcomes[5] as well as monitoring in the first 72 hours of life in extremely preterm infants[4]. While these studies will likely provide support for applying NIRS as routine care for preterm infants, there is data lacking when infants are born at altitude. It is unknown if the increased altitude in places such as Albuquerque and Denver would result in a different range of expected values with NIRS monitoring. Thus, we proposed a prospective observational study in which we apply NIRS monitoring to

PROTOCOL TITLE:

infants born <32 weeks' gestation for the first 96 hours of life to assess the cRSO2 as well as outcome information for the infant.

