### **11. Multi-Site Research – N/A**

### **12. Study Procedures**

Any infant that is born at <32 weeks' gestational age and does not meet exclusion criteria as described above will be considered for the study. The mother/guardian must speak English as we do not have the resources to translate the documents, nor could we obtain consent appropriately. If an infant is born at another hospital and transferred to UNMH, they will be considered for the study only if the mother/guardian is physically present.

The study will be described following the consent script (attached) and if consent is obtained, the infant will then be given a study identifier (ex. NIRS-1). The "NIRS-1" component of the identifier will be the infant's number used so that identifying information can be removed. For sub-analysis, the infants will be divided into 3 groups to assess the impact of gestational age on the measurements. Specifically, the 3 groups will be divided into the following ages: Group 1: 23 to ≤26 weeks' gestation; Group 2: >26 weeks' gestation to ≤29 weeks' gestation; Group 3: >29 weeks' gestation to 31 6/7 weeks' gestation.

The NIRS device will be applied after the infant is admitted to the Newborn Intensive Care Unit (NICU) at UNMH (ideally within the first 12 hours of life). The device will remain in place, with routine skin care management during care times, for the first 96 hours of life and then removed. This will allow 72-96 hours of data collection, depending on the timing of the placement of the NIRS device in relation to the birth time. The SpO2 (routine oxygen saturation monitoring) information will be collected at the same time so that the relative cerebral fractional tissue oxygen extraction can be calculated. The data output will not be visible to the clinical team, so there will not be any incidental clinical interpretation of this data.

To apply the device, a trimmed piece of Mepitel (MoInlycke), which is a translucent skin dressing, will be placed with the hydrocolloid adhesive-backed NIRS sensor placed

PROTOCOL TITLE:

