directly onto the Mepitel. The sensor will then be placed with the skin dressing onto the central forehead of the infant. The sensor will be plugged in to ensure that signal strength is appropriate. There will be daily inspection of the sensor site by the research team, with the area monitored by the bedside nurse with each care-time (usually every 3 hours). The area will be monitored for erythema or irritation of the skin around the sensor, and the sensor will be removed or replaced if necessary. We will avoid lifting up the sensor unless necessary for removal or repositioning. Care will be taken to avoid pressure on top of the sensor. After the infant is 96 hours of age, the sensor will be removed. Adhesive remover or a warm moist cloth will be used to slowly remove the sensor from the skin. The sensor will then be discarded after use. The NIRS probe (circled in red) is shown below in this sample image taken from van Bel, et al[6]. Additionally, the NIRS probe is plugged into a NIRS monitor, which is then plugged into the Phillips monitor if desired. We currently have 6 of the devices which connect the NIRS to the Phillips monitor, however need to purchase the NIRS monitor and the NIRS probes.

Information will be collected from the medical record at time of enrollment as well as at the time of infant discharge. This information will include: gestational age at birth, birth weight, mode of delivery, sex of infant, maternal complications during pregnancy (including pre-eclampsia, chorioamnionitis, hypertension, diabetes, thyroid disease, and cervical insufficiency), maternal medications during pregnancy, resuscitation required at birth including if chest compressions were done, length and type of respiratory support infant required, intraventricular hemorrhage, necrotizing enterocolitis, patent ductus arteriosus and if treatment was used, chronic lung disease, retinopathy of prematurity, any surgeries that were completed during the hospitalization, sepsis, hospital length of stay, time to full volume nipple of feeds, and death if applicable. The data obtained during the NIRS recording will be collected and analyzed to determine the average cerebral regional oxygen saturation. The relative cerebral fractional tissue oxygen extraction will be calculated. The blood pressure and heart rates of each infant that are normally obtained for clinical purposes will be extracted from the patient charts during the time of the NIRS monitoring.

PROTOCOL TITLE:

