### **13.Data Analysis**

The cerebral regional oxygen saturation data will be averaged for each infant. All male and female data will be analyzed separately and the compared to determine any statistical differences that are present between sexes. NIRS parameters will be summarized as median and interquartile ranges. The relative cerebral fractional tissue oxygen extraction will be calculated using the following equation:  $(SpO_2 - rScO_2)/SpO_2$ .

As described above, there will be a sub-analysis of the infants enrolled based on gestational age. Specifically, the 3 groups will be divided into the following ages: Group 1: 23 to  $\leq 26$  weeks' gestation; Group 2:  $>26$  weeks' gestation to  $\leq 29$  weeks' gestation; Group 3:  $>29$  weeks' gestation to 31 6/7 weeks' gestation. Comparisons among different groups will be analyzed by one-way ANOVA followed by Dunn's method. Categorical data will be analyzed using Fisher's test. Spearman's rank correlation coefficient will be used to calculate correlations between cerebral regional oxygen saturation, relative cerebral fractional tissue oxygen extraction and gestational age. Values of  $p < 0.05$  will be considered statistically significant.

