#### B. Neonates of Uncertain Viability or Nonviable Neonates

PROTOCOL TITLE:

*Complete this checklist if the subject population will include neonates of uncertain viability.*

Provide justification for each of the following:

1. Where scientifically appropriate, preclinical and clinical studies have been conducted and provide data for assessing potential risks to neonates.  
*Prior research has been conducted using the NIRS technology in this patient population. There have been minimal risks noted to the neonates that have the sensor in place. However, the use of this technology has not been reported at high altitude, which has the potential to directly impact the results.*
2. Each individual providing consent is fully informed regarding the reasonably foreseeable impact of the research on the neonate.  
*Each mother / guardian will provide consent and be fully informed. We expect there to be no direct benefit to the neonates in the study, however the results may inform future use in the NICU that may become routine.*
3. Individuals engaged in the research will have no part in determining the viability of a neonate.  
*The use of this technology will not impact the viability of the neonate, and the research team will not be determining the viability of the neonate in relation to this study.*
4. The research holds out the prospect of enhancing the probability of survival of the neonate to the point of viability, and any risk is the least possible for achieving that objective, or, the purpose of the research is the development of important biomedical knowledge which cannot be obtained by other means and there will be no added risk to the neonate resulting from the research  
*The results from this study have the potential to impact the routine use of this technology in the NICU and may have the ability to note if/when an infant is having an acute change in cerebral blood flow which may reflect an intraventricular hemorrhage. The purpose of this research cannot be obtained by other means and there will be no added risk to the neonate resulting from the research.*

Verify each of the following:

1. The research will not terminate the heartbeat or respiration of the neonate  
 True  
 False
2. There will be no added risk to the neonate resulting from the research  
 True

PROTOCOL TITLE:

False

---

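### The planned spread of cRSO2 is that of multi-day infant averages, so it is narrower than the range of values a continuous monitor shows; report an epoch-level distribution beside it

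*Combined protocol and SAP*

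**What the plan says.** - **Target.** Section 1 (Objectives) gives the purpose as "to determine if the range of “normal” values is different than those obtained at sea level". The deliverable is therefore a range as well as a typical value.
- **Reduction of the recording.** Section 13 begins: "The cerebral regional oxygen saturation data will be averaged for each infant". Section 12 (Study Procedures) agrees: "The data obtained during the NIRS recording will be collected and analyzed to determine the average cerebral regional oxygen saturation". Neither section names an hour, a day or any other window.
- **Summary.** Section 13 continues: "NIRS parameters will be summarized as median and interquartile ranges". It names no outer centiles and no reference-interval method.
- **Length of recording.** Section 12 states: "This will allow 72-96 hours of data collection, depending on the timing of the placement of the NIRS device". Section 4 admits an infant to the final sample after at least 48 hours of monitoring.
- **Within-infant variation.** Section 2 (Background) expects fluctuations in cerebral blood flow in these infants. Aim 2 in Section 1 will compare outcomes with each infant's average cRSO2 and with its fluctuation. Section 13 gives no measure of fluctuation.
- **Foreseen use.** Section 2 describes NIRS as "a technology that can provide continuous, non-invasive monitoring of oxygenation in tissue". Section 19 looks ahead to routine use. The neonates checklist (Section 38, part B) adds that the technology "may have the ability to note if/when an infant is having an acute change in cerebral blood flow".

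**The concern.** An average over two to four days removes nearly all the movement of cRSO2 within an infant. Quartiles taken across such averages describe how infants differ from one another in their long-run level. They do not describe the values that appear on the monitor from hour to hour, yet the second meaning is the natural one for a range of normal values from a continuous device.

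What is at stake is the meaning of the published range. If infant averages are reported without that label, a reader may set a current reading against them and find ordinary readings outside the range more often than its centiles imply. The recordings could describe both kinds of variation, but Section 13 uses them for only one.

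**Working it through.** The plan has no figure to reproduce: it gives no SD for cRSO2, and Section 5 supports the sample of 100 only by reference to a similar study. The check is a variance decomposition with assumed SDs.

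**Inputs**
- From the documents: one average per infant; 72-96 h of recording planned, at least 48 h for inclusion; summary by quartiles.
- Assumed: between-infant SD (B) of 5, 6 or 7 points; within-infant SD (W) of 3, 5, 6 or 8 points, with 2 as a low case; normal values. The centre cancels out of the shifts.

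**Formulas**
- SD of single readings = √(B² + W²).
- SD of infant averages = √(B² + W²/m), where m is the effective number of independent readings per infant. For large m this is close to B.
- Lower quartile = centre − 0.674 × SD. The shift is therefore 0.674 × (SD of readings − SD of averages).
- Share of readings below the averages' lower quartile = Φ(−0.674 × SD of averages / SD of readings).

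**Direction.** √(B² + W²) exceeds √(B² + W²/m) whenever W > 0 and m > 1. The SD of averages must be the smaller, whatever the shape of the distribution.

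**Size for the planned IQR (large m)**

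| B | W | SD of readings | Shift in lower quartile (points) |
|---|---|---|---|
| 7 | 3 | √58 = 7.62 | 0.674 × 0.62 = 0.4 |
| 6 | 6 | √72 = 8.49 | 0.674 × 2.49 = 1.7 |
| 5 | 8 | √89 = 9.43 | 0.674 × 4.43 = 3.0 |
| 6 | 2 | √40 = 6.32 | 0.674 × 0.32 = 0.2 |

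The first and third rows are the extremes of the assumed grid. At B = W = 6 the share of readings below the averages' lower quartile is Φ(−0.674 × 6/8.49) = Φ(−0.477) ≈ 32%, against 25% by definition for the quartile of readings.

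**Sensitivity to autocorrelation.** Strong autocorrelation lowers m. At B = W = 6 and m = 12, the SD of averages is √39 = 6.24 and the shift is 0.674 × (8.49 − 6.24) = 1.5 points, so the result changes little.

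**Sensitivity to skew.** A simulation used 4,000 infants with 336 autocorrelated readings each, centre 70 and B = W = 6. With symmetric readings the lower quartile was 66.0 for averages and 64.4 for readings. With left-skewed readings it was 65.6 and 64.9. Skew thus cut the quartile gap from 1.6 to 0.7 points. It widened the gap at the 2.5th centile: 57.6 against 51.2, compared with 57.9 against 53.3 for symmetric readings. The averages had the higher lower limit in every scenario run.

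**Location.** With infants weighted equally, the mean of infant averages equals the mean of readings. Under the normal model the medians agree too. In the skewed simulation they differed slightly (69.9 for averages, 70.6 for readings).

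**The case against.** - **One value per infant is a sound unit.** It avoids treating repeated readings as independent, and it suits the group comparisons, the correlations and Aim 2. This stands, and the infant average should stay for those analyses.
- **Section 13 neither says that the whole recording is averaged nor calls the IQR a normal range.** This is true. The reading rests on the absence of any shorter window, on the matching sentence in Section 12, and on the lack of any other summary in Section 13 that could answer the objective.
- **Aim 2 keeps fluctuation as a variable.** It does, but for comparison with outcomes. It has no defined measure and does not enter the range.
- **Infant averages may be the right match for sea-level values.** They would be if those values were averaged over a similar period. The documents do not give that period, so the mismatch could run either way.
- **Bedside harm is remote.** This is a pilot with data hidden from clinicians, and no passage proposes the IQR as an alarm limit. This stands. The point concerns what the reported range means.

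Two stronger readings are tempting. First, a reader might compute a 95% range: with both SDs at 6, its lower limit shifts by 1.96 × (8.49 − 6) = 4.9 points, and 16.6% of readings instead of 5% fall outside. The plan contains no such interval, so these figures do not describe it. Second, a reader might infer that averaging could hide or reverse the hypothesised lower cRSO2. That hypothesis is most naturally read as one about location, averaging leaves the mean where it is, and no comparison of lower limits is planned.

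**Conclusion.** The point holds as a matter of what the summary describes. As written, Section 13 would answer an objective about the range of normal values with the spread of multi-day infant averages, which omits nearly all within-infant variation. That the spread is too narrow for monitored values is certain if cRSO2 varies within an infant, and the protocol expects it to.

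The size is not known. Under the assumed SDs and normal values, the lower quartile sits about 0.4-3.0 points too high for single readings, 1.7 points with both SDs at 6. It is close to negligible if the within-infant SD is near 2, and smaller under left skew. Outer centiles would shift more, but the plan names none.

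The documents do not support a claim that the comparison of location with sea level is biased. This is a cheap improvement to the analysis plan, and the planned per-infant analyses remain valid.

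**What to change.** In Section 13:

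1. Keep the per-infant average for the group comparisons, the correlations and Aim 2. Label its median and IQR as describing infant averages over the recording.
2. Beside it, report the distribution of cRSO2 over an epoch fixed in advance, for example hourly means, with each infant weighted equally.
3. Report the between-infant and within-infant SDs, with confidence intervals from a bootstrap that resamples infants. A random-intercept model is one way to obtain the SDs. Because it ignores autocorrelation, skew and any trend with age, show the empirical distribution as well.
4. State that the epoch-level interval applies to values averaged over that epoch. Variation within the epoch is still removed, so the interval will not close the whole gap to single readings.
5. In any contrast with sea-level values, use whichever summary matches the averaging period of the reference, and state that period.

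The cost is some wording, modest programming and a decision on epoch length before the data are analysed. No extra infants, recordings or procedures are needed. The downside is a wider interval.

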### **5. Number of Subjects**

PROTOCOL TITLE:

This is a single site, observational study. The goal number of patients to be recruited is 100. A similar study that evaluated an older cohort (30 weeks' gestation to 42 weeks' gestation) was able to find significant differences with a sample size of 100[3]. Given the number of extremely preterm infants (<28 weeks' gestation) born at UNMH varies from 18-30 per year, we expect to reach goal enrollment within a 2-year period, as we are including up to 32 weeks' gestation.

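### The objective is a range of normal cRSO2 values, but Section 13 plans only a median and interquartile range, so as planned no reference range will be reported

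*Combined protocol and SAP*

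**What the plan says.** Section 1 (Objectives) gives the purpose as "to determine if the range of “normal” values is different than those obtained at sea level". Section 2 (Background) frames the open question in the same way, as one about the span of values to expect at altitude. The hypothesis in Section 1 concerns location: cRSO2 "will be lower than the normative values that have been previously described". Neither section gives those values or names their source as the comparator.

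Section 13 (Data Analysis) first reduces the recordings to one number per infant: "The cerebral regional oxygen saturation data will be averaged for each infant". It then states that "NIRS parameters will be summarized as median and interquartile ranges". The rest of the section covers a comparison by sex, ANOVA followed by Dunn's method across gestational-age groups, Fisher's test, Spearman correlations and a 0.05 significance level.

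Section 12 (Study Procedures) adds only the average cRSO2 and the fractional extraction, and says that "the infants will be divided into 3 groups to assess the impact of gestational age on the measurements". Section 7 (Study Endpoints) ties the primary endpoint to completing enrolment and expects nothing exploratory beyond the Aims. No section plans an outer centile, a reference interval, a confidence interval for a limit, or a definition of normal.

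**The concern.** The quantity in the objective and the quantity in the analysis are different. A range of normal values is a pair of outer limits that contains most infants. An IQR is the middle half of the sample. None of the other planned analyses supplies the missing limits: the group and sex comparisons test for differences, and a rank correlation gives no limit at any gestational age.

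If Section 13 is followed exactly, the study ends with a centre and a middle-half spread, neither with a stated precision, and leaves the question about the range unanswered. Limits added after the data are seen would leave the choice of centile, model and comparator open to selection. This matters because Section 1 presents the result as something to settle before NIRS is generally adopted, and Section 19 expects it to support routine use.

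**Working it through.** **Inputs.** From the documents: one mean per infant and median/IQR (Section 13); "The goal number of patients to be recruited is 100" (Section 5); three gestational-age groups (Section 12). Assumptions: per-infant means are roughly normal; groups are of equal size, so about 100/3 = 33 each; SD is 5 to 10 points for illustration, since the documents give none.

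**The plan's own figure.** The target of 100 rests on the precedent of a study in an older cohort. There is no SD, effect size, power or precision target behind it, so it cannot be reproduced, and it does not show how well a limit would be estimated.

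**1. Coverage.** The 25th to 75th centile contains 50% of infants by definition, whatever the distribution.

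**2. Width, if normal.**
- IQR: 2 × 0.6745 = 1.349 SD
- 90% range: 2 × 1.645 = 3.29 SD; 1.349/3.29 = 41%
- 95% range: 2 × 1.960 = 3.92 SD; 1.349/3.92 = 34%

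For an SD of 5 to 10 points the IQR is 6.7 to 13.5 points wide and the 95% range 19.6 to 39.2 points wide.

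**3. Precision of a normal-theory limit.** SE = SD × √(1/n + z²/(2n)); the 95% CI half-width is 1.96 × SE.

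| Limit | n | SE (SD) | 95% CI (SD) |
|---|---|---|---|
| 2.5th or 97.5th (z = 1.960) | 100 | √(0.0100 + 0.0192) = 0.171 | ±0.335 |
| 2.5th or 97.5th | 33 | √(0.0303 + 0.0582) = 0.298 | ±0.583 |
| 5th or 95th (z = 1.645) | 100 | √(0.0100 + 0.0135) = 0.153 | ±0.301 |

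Using 2(n − 1) in place of 2n gives ±0.336 and ±0.589 for the first two rows. For an SD of 5 to 10 points the first row is about ±1.7 to ±3.4 points and the second about ±2.9 to ±5.8 points.

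**4. Can the limits be estimated without a distributional assumption?** A distribution-free interval is bounded by ordered observations, so its coverage cannot exceed the probability that the sample minimum lies below the true centile, 1 − (1 − p)^n.
- 2.5th centile, n = 100: 1 − 0.975^100 = 0.92. This is below 0.95, so no 95% interval with a finite lower bound exists. The 97.5th centile is the mirror image. The value first reaches 0.95 at n = 119.
- 5th centile, n = 100: 1 − 0.95^100 = 0.994. An interval exists: the 1st to the 10th ordered value has 96.6% coverage.
- 5th centile, n = 33: 1 − 0.95^33 = 0.82. No 95% interval with a finite lower bound exists within a single group.

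So 5th and 95th centiles are estimable overall, 2.5th and 97.5th centiles need a distributional model, and outer limits read from three separate groups are poorly supported either way.

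**The case against.** The strongest reply is that nothing is lost. Section 13 keeps a mean for every infant, so any centile can be computed later. A reader might infer that the study cannot report a range; the documents do not support that. The omission is in the planned output, and no new data are needed to repair it.

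A reader might also infer that the plan labels half of its infants abnormal. It does not. Section 13 uses the IQR only as a summary, no section calls it a normal range or classifies an infant by it, and clinicians are kept from the readings. That half of the infants lie outside is true of every IQR and does harm only if the IQR is later read as limits.

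Nor do the documents show that the sea-level comparison will be false. They do not say how the published norms are expressed. If those are medians and IQRs, like would be compared with like. The risk is conditional: the plan names no reference and does not require matching centiles, so it does not rule out a mismatch.

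Finally, the stated hypothesis is about lower values, and a median addresses that, although Section 13 specifies no test against the norms. All of this stands and narrows the point. It does not supply the range that Section 1 asks for.

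**Conclusion.** The point holds as an omission from the analysis plan: as written, Section 13 will not produce a reference range, although a range is what the objective names. The 50% coverage needs no assumption. The 34% and 41% width ratios and the precision figures assume approximate normality; the figure for a group of 33 also assumes equal groups. The n = 100 figures assume that all recruited infants are analysed, whereas Section 4 keeps only those with at least 48 hours of monitoring, so intervals may be somewhat wider.

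One further limit applies to any repair. Section 4 admits infants who need transfusion, and Section 18 expects serious complications, particularly in the youngest group. A reader might take outer centiles as limits for healthy infants. They would describe this enrolled cohort, and should be labelled so.

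**What to change.** Amend Section 13, before the data are examined, to make the Aim 1 output a central reference interval for per-infant mean cRSO2 and for fractional extraction:

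- Report the 5th, 50th and 95th centiles, each with a 95% CI. Use the 2.5th and 97.5th only as normal-theory limits, after checking the distribution and transforming if needed.
- Model the limits on continuous gestational age, which is already collected, by quantile regression at the 5th and 95th or by regression with normal-theory limits. Do not read outer limits from the three groups.
- Name the sea-level reference and compare only matching centiles with it.
- State the averaging period to which the limits refer, and describe them as limits of this enrolled cohort.
- Keep median and IQR as description.

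The cost is a few lines of text and no new data. The price is visible uncertainty: about ±0.33 SD for each 2.5th or 97.5th normal-theory limit at n = 100, and more at the extremes of gestational age. Reading the limits from separate groups would cost more, at about ±0.58 SD in a group of 33.

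### Two minor faults in Section 13: the Spearman list takes in cRSO2 against an index computed from cRSO2, and one-way ANOVA is followed by Dunn's method, usually a rank-based procedure.

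*Combined protocol and SAP*

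**What the plan says.** All the methods are in Section 13 (Data Analysis) of the combined protocol and SAP. cRSO2 is averaged to one value per infant.

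- **Extraction index.** "The relative cerebral fractional tissue oxygen extraction will be calculated using the following equation": (SpO2 − rScO2)/SpO2. Section 12 explains that the routine SpO2 "information will be collected at the same time so that the relative cerebral fractional tissue oxygen extraction can be calculated".
- **Correlations.** Spearman's "rank correlation coefficient will be used to calculate correlations between cerebral regional oxygen saturation, relative cerebral fractional tissue oxygen extraction and gestational age". No pairs are named. The section closes with a general significance rule of p < 0.05.
- **Group comparison.** "Comparisons among different groups will be analyzed by one-way ANOVA followed by Dunn's method". The groups are the three gestational-age bands of Section 12: "For sub-analysis, the infants will be divided into 3 groups to assess the impact of gestational age on the measurements".
- **Summaries.** "NIRS parameters will be summarized as median and interquartile ranges".

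Section 13 does not mention Kruskal-Wallis, ANOVA on ranks, a check of distribution, or which form of Dunn's method is meant.

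**The concern.** **Correlations.** Three variables listed together with no pairs named give three pairs on a plain reading. One of them sets cRSO2 against a quantity calculated from cRSO2. A test of zero correlation for that pair is close to certain to reject whatever the physiology, yet the p < 0.05 rule would label the result significant and it could be reported as a finding.

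**Group comparison.** One-way ANOVA tests equality of means. Dunn's method, in its usual sense, compares mean ranks after Kruskal-Wallis. Taken literally, the overall test and the pairwise tests address different hypotheses and can disagree for that reason alone. The rest of the section (median and interquartile range, rank correlation) points towards ranks, which makes ANOVA the odd item.

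At stake is how the gestational-age sub-analysis and the secondary correlations are read.

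**Working it through.** The documents give no mean, SD, distribution or expected correlation, and the target of 100 infants rests on the size of an earlier study. There is therefore no stated figure to reproduce, and every input below except N=100, the three groups and the 0.05 level is an assumption. Tests are taken as two-sided.

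**1. The coupled pair**

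Extraction = (SpO2 − rScO2)/SpO2 = 1 − rScO2/SpO2. Here rScO2 is taken to be the same quantity as cRSO2; both labels appear, but only one cerebral saturation is measured. At fixed SpO2 the index is strictly decreasing in cRSO2, so Spearman rho is exactly −1. Variation in SpO2 loosens this.

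To first order, let c and s be SD/mean for cRSO2 and SpO2, and r their correlation. The correlation of cRSO2 with extraction is then approximately −(c − r·s)/√(c² + s² − 2·r·c·s). Assume mean cRSO2 70 and mean SpO2 92. The simulated Spearman values (200,000 draws, SpO2 capped at 100) are alongside.

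| cRSO2 SD | SpO2 SD | r | c | s | First-order value | Simulated rho |
|---|---|---|---|---|---|---|
| 10 | 1.5 | 0 | 0.143 | 0.016 | −0.99 | −0.99 |
| 5 | 5 | 0 | 0.071 | 0.054 | −0.80 | −0.79 |
| 5 | 5 | 0.5 | 0.071 | 0.054 | −0.69 | −0.69 |
| 3 | 5 | 0 | 0.043 | 0.054 | −0.62 | −0.61 |
| 3 | 5 | 0.5 | 0.043 | 0.054 | −0.32 | about −0.33 |
| 3 | 5 | 0.8 | 0.043 | 0.054 | 0.02 | −0.03 |

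The first three rows span the main grid (cRSO2 SD 5–10, SpO2 SD 1.5–5, r up to 0.5). The last three are corner cases in which SpO2 varies more than cRSO2.

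The rho needed for p < 0.05 is t/√(N − 2 + t²). At N=100, t = 1.984, giving 1.984/√(98 + 3.94) = 0.20. It is 0.28 at N=50 and 0.36 at N=30. In the settings simulated on the main grid, the pair was significant in 100% of studies at N=50 and N=100, and in at least 99% at N=30.

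**2. ANOVA followed by Dunn's**

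Simulation assumptions: SD 8; group shifts 0/2.5/5; groups of 33/33/34 or 20/35/45; Bonferroni adjustment of the pairwise tests; pairs counted only after a significant overall test; 20,000 replicates (standard error at most √(0.25/20,000) = 0.35 points). Each cell gives the two group splits in that order.

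| Result (% of studies) | Normal data | Skewness −1.75 |
|---|---|---|
| ANOVA significant, no Dunn pair significant | 7.4; 8.1 | 1.5; 2.5 |
| Overall test and at least one pair: as written | 53.8; 47.1 | 61.2; 53.5 |
| Same: Kruskal-Wallis plus Dunn's | 55.1; 48.4 | 77.4; 69.1 |
| Same: ANOVA plus Bonferroni t-tests | 58.1; 51.2 | 59.8; 52.0 |

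- **Mismatch.** For normal data, matched procedures leave a significant overall test with no significant pair in about 3–4% of studies. The excess from mixing is therefore about 4 points (3.2–4.3 over shifts 0/2/4 to 0/3/6). At skewness −1.75 there is no excess. If Dunn's is unadjusted, the 7–8% falls to 0.2–0.5%.
- **Choice of overall test.** Over the same shifts, Kruskal-Wallis power minus ANOVA power is −2 to −3 points for normal data, 0 to +1 at skewness −0.6, +3 to +5 at −0.95, and +14 to +17 at −1.75.
- **No true difference.** ANOVA rejects in 4.8–5.3% of studies, and ANOVA plus a Dunn pair in 2.7–3.6%.

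**The case against.** **The authors probably mean only the gestational-age pairs.** Section 12 gives gestational age as the purpose of the sub-analysis, and the Background notes that "some initial studies have shown a negative correlation between cerebral regional oxygen saturation" and gestational age. No aim or endpoint names cRSO2 against extraction. This is a fair reading, and under it the first point disappears, since both gestational-age correlations are sound. But Section 13 does not limit the list, so the limit has to be written in.

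**The coupling is not always strong.** This stands. The corner rows above show rho shrinking towards zero when SpO2 varies more than cRSO2 and the two are closely correlated. The range −0.69 to −0.99 belongs to the assumed grid and is not a bound. The size of rho also carries some information about SpO2; it is the test against zero that does not inform.

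**The Dunn's wording may be shorthand.** It may stand for ANOVA on ranks, or for Bonferroni-Dunn comparisons of means. If so, only the name is unclear. Even on the literal reading, with normal data the plan loses only 1.3 points to Kruskal-Wallis plus Dunn's (55.1 − 53.8; 48.4 − 47.1), and the 7–8% figure depends on a Bonferroni adjustment that the plan does not state. Both facts stand and keep the point minor.

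**The large gap under skewness is not caused by the mismatch.** Correct. It comes from using ANOVA rather than Kruskal-Wallis, at a skewness that is assumed.

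A reader might go further and infer that the main analysis is invalid or that false positives are inflated. The documents do not support either. The altitude question does not use these tests, and the group comparison keeps its nominal error rate.

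**Conclusion.** Both points hold, and both are minor.

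1. On its plain reading, Section 13 tests a pair that is coupled by formula. Under plausible but assumed SDs the result is almost always significant at N=100, and that p-value should not be offered as evidence of a physiological relation.
2. Unless ANOVA on ranks or Bonferroni-Dunn on means was meant, the overall and follow-up tests do not match. Assuming normal data and adjusted Dunn's, this adds about 4 points to the chance of a significant overall test with no significant pair. As a separate matter, strong assumed skewness would cost ANOVA about 14–17 points of power against Kruskal-Wallis.

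The effect is confined to the gestational-age sub-analysis and the secondary correlations. Confidence is medium: the algebra is certain, but the authors' intent is open and every magnitude rests on inputs that the documents do not supply.

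**What to change.** Two wording changes in Section 13, with no new data.

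1. *Spearman correlations will be tested for cRSO2 with gestational age and for extraction with gestational age.* Report cRSO2 with extraction, if at all, descriptively and without a p-value. This costs nothing.
2. *Kruskal-Wallis test followed by Dunn's method with Bonferroni-adjusted pairwise p-values.* The cost is about 2–3 points of overall-test power if the per-infant averages are exactly normal. The chance that the overall test and at least one pair are both significant does not fall even then (53.8 to 55.1%; 47.1 to 48.4%).

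If means are truly intended, ANOVA with a named mean-based pairwise procedure would also be coherent. It does best for normal data (58.1; 51.2%), but under strong skewness it falls slightly below the present text (59.8; 52.0% against 61.2; 53.5%), so the rank-based version is preferred. It also fits the median and interquartile-range summaries already planned.
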